5. REGISTRATION PROCEDURES

5.1. Identification of subjects:

Patients diagnosed with documented progressive metastatic CRPC disease who

are visiting Oncology Clinic at NYPH-Cornell Campus for their standard of care visit, will be approached for recruitment for this study. Investigators or delegates under their direct supervision may perform pre-screening of these potential subjects.

5.2. Consent process

Potential subjects will have a discussion with the investigator/delegate including the rationale for the study, investigational nature of the protocol and study drug and the voluntary nature of participation, potential risks and benefits, alternatives to participation, and study procedures. Individuals will have the opportunity to read the written informed consent document at their leisure (preferably outside of the clinical area for > 1 day) and the opportunity to have questions answered in a private location with the understanding that should they decide not to participate, they will still be able to receive any available standard of care therapy. Potential subjects will also have the opportunity to obtain the advice of their treating physician. Investigators or delegates under their direct supervision will verify the subject's understanding of the investigational and voluntary nature of the study, the potential risks and benefits, study procedures, and alternatives prior to signing of the written informed consent.

5.3. Central Patient Registration

Subjects will be assigned a sequence number for the protocol and will be centrally registered with the Weill Cornell Medicine (WCM), Division of Hematology and Medical Oncology Clinical Research Office with the following documents:

- WCM Patient registration form
- First and last page of the fully executed informed consent form (including HIPPA), plus additional pages if checkboxes for correlative studies are required.
- Eligibility checklist signed and dated by investigator and research nurse
- Documentation of any eligibility waivers granted
- Entry of screening information into WCM web-based system

Central registration information is reviewed and entered into the HemOnc centralized research database. Documentation of patient registration will be confirmed prior to release of study agent by nuclear medicine.

6. STUDY PROCEDURES

Screening assessments and study procedures outlined in this section can only be performed after obtaining informed consent.

All on-study visits and dosing should be scheduled from Day 1 (date of the first infusion) on the study. It is very important that protocol procedures are performed at the time-points stipulated below. When it is not possible to perform the study visit at the exact time-point, the visit maybe performed within the acceptable visit window as defined in the visit-specific section below.

After obtaining informed consent from the enrolled subject(s), screening and study related treatment procedures will be performed as outlined in Table 8 and described in detail in Section 6.1.

7. Schedule of Evaluations Table 8: Schedule of trial events:

	Screening	Treatment Visit 1 (Day 1)	Imaging visit (Day 8±1)	Treatment Visit 2 (Day 15 ±1)	F/U Visit 1 (Day 22±3)	F/U Visit 2 (Day 29 ±3)	F/U Visit 3 (Day 43 ±3)	F/U Visit 4 (Day 57 ±3)	F/U Visit 5 (Day 71 ±3)	Scan Visit (Day 85±7)	Short-Term F/U ^k	Progression	Long-Term F/U
Informed Consent	x												
Demographics	x												
Medical History	x	x	x	x	x	x		x		x	x	x	
Physical Exam	x	x	x	x	x	x		x		x	x	x	
Performance Status	x	x	x	x	x	x		x		x	x	x	
Vital Signs ^a	x	x	x	x	x	x		x		x	x	x	
PRO ^l	x	x	x	x	x	x		x		x	x ^l	x	
CBC with diff, plts ^b	x	x	x	x ^c	x	x	x	x	x	x	x	x	
Serum Chemistry ^d	x	x	x	x	x	x	x	x	x	x	x	x	
PSA	x	x		x		x		x		x	x	x	
LDH		x		x		x		x		x	x	x	
Testosterone	x									x		x	
CTC Count ^e	x	x ^e								x			
CTC for Research ^f	x	x ^f								x			
Cell-Free DNA Research sample ^g	x	x ^g								x		x	

Immune research sample ^m	x	x ^m								x				
⁶⁸ Ga-PSMA infusion & PET CT ⁿ	x									x				
Radiographic evaluation ^h	x									x	x ^h			x ^h
¹⁷⁷ Lu-PSMA-617 infusion		x		x										
¹⁷⁷ Lu-PSMA-617 Planar/SPECT imaging ⁱ			x ⁱ	x ⁱ										
Archival Tissue	x													
Adverse Event Monitoring		x	x	x	x	x		x		x	x	x		
Concurrent Medications	x	x	x	x	x	x		x		x	x	x		
Survival Assessment ^j											x	x		

- a: Vital signs will include height and weight during screening and at least weight thereafter
- b: Any subject with grade >2 neutropenia or thrombocytopenia at any time point will be followed at least weekly until resolution to grade 1
- c: Any subject with grade ≥ 2 neutropenia or thrombocytopenia at Treatment Visit 2 will initially not be eligible to receive the second ^{177}Lu -PSMA-617 injection. The dose will be held until the toxicity has resolved to grade 1 for a maximum of 2 weeks. If the toxicity has not resolved after 2 weeks, the dose will be discontinued.
- d: CMP (with direct bilirubin in subjects with known Gilbert's syndrome)
- e: CTC enumeration via CellSearch methodology may be obtained during screening or prior to Treatment Visit 1
- f: CTC collection for research purposes may be performed during screening or prior to Treatment Visit 1: two 2.3% sodium citrate "light blue top" tubes (5.4 mL whole blood)
- g: Cell-Free DNA BCT[®] may be obtained during screening or prior to Treatment Visit 1 and will be whole blood collection in a tube intended for collection, stabilization and transportation of cell-free plasma DNA. 10 mL tube will be used for collecting whole blood for research purposes
- h: Radiographic evaluation will include bone scan, CT/MRI of abdomen/pelvis, and Chest x-ray (CXR waived if CT/MRI includes chest). Following mandatory repeat imaging with Scan/Efficacy visit, continued repeat imaging is recommended approximately 12 weeks until radiographic progression as part of standard care.
- i: Planar/SPECT imaging one week after the ^{177}Lu -PSMA-617 1st dose infusion in all subjects. Optional imaging will be performed on consenting subjects between Treatment Visit 1 (Between D2-D4) or prior to Treatment Visit 2 (D15 ± 1).
- j: Survival assessment and relevant medical history to be collected until death
- k: Short-term follow up to be completed q4 weeks following the scan visit until 6 months from the 1st treatment visit. Subjects who are progression-free at 6 months will continue with q4-week labs and q12-week standard imaging per guidelines (as in h above).
- l: PRO = patient reported outcomes = BPI-SF and FACT-P; to be performed at time points specified during treatment phase, then q12 weeks (at imaging time points) during short-term follow up until radiographic progression
- m: serum for immune assays; 1 sample to be collected at any time during screening prior to Treatment Visit 1, then again during Scan/Efficacy visit
- n: PSMA imaging is planned for all subjects. However, in the event of unavailability of radiotracers, subjects will be allowed to enroll and receive treatment without PSMA imaging. Optional repeat ^{68}Ga -PSMA PET/CT will be repeated prior to treatment or 6-48 hours after treatment in consenting subjects.

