6.1.1. Screening Visit

The following procedures must be completed no more than 1 month prior to enrollment and no more than 4 weeks following enrollment.

- Informed Consent
- Demographics
- Medical History
- Previous therapy
- Surgical report will include date and type of surgery +/- lymphadenectomy
- Radiotherapy report will include modality of therapy with prescribed dose and field and dates of therapy
- Previous systemic (hormonal, chemo, other) therapy – drugs, doses, dates of therapy
- Complete Physical Exam including height and weight
- Brief Pain Inventory
- Vital Signs
- ECOG Performance Status
- CBC with differential and platelet count
- CMP (with direct bilirubin with known Gilbert's syndrome)
- PSA
- Testosterone
- CTC count via CellSearch methodology (may be collected prior to treatment C1D1, do not need to repeat if has known result within 1 month of C1D1)
- CTC for Research (may be collected prior to treatment C1D1)
- Cell-Free DNA BCT® Research blood sample (may be collected prior to treatment C1D1)
- Immune research blood sample (may be collected prior to treatment C1D1)
- CT or MRI (abdomen-pelvis), up to 1 month prior to enrollment
- Bone scan, up to 1 month prior to enrollment
- Any confirmatory tests to assess equivocal results of bone scan should also be completed within a month of enrollment
- CXR, up to 1 month prior to enrollment (CXR waived if CT chest performed)
- Single intravenous dose of ^{68}Ga -PSMA-HBED-CC ($5\pm 2\text{mCi}$ or $185\pm 74\text{MBq}$) at least 1 week prior to ^{177}Lu -PSMA-617 infusion
- ^{68}Ga -PSMA-HBED-CC PET/CT scan to confirm the PSMA expression at the tumor site(s). PET/CT scans will be obtained 1 to 3 hours after the infusion of ^{68}Ga -PSMA-HBED-CC. Optional repeat ^{68}Ga -PSMA-HBED-CC injection and PET/CT prior to treatment in consenting subjects for research purposes.
- Archival tissue for PSMA expression and genomic studies to identify DNA

damage

Screening (except required ^{68}Ga -PSMA-HBED-CC PET/CT scan) and visit #1 may occur on the same day provided results are available, all entry criteria are met, and the subject is registered on the study prior to dosing. In this instance, duplicate procedures do not need to be performed. ^{68}Ga -PSMA-HBED-CC should occur at least 2 days prior to Treatment Visit #1.

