9.2. Imaging Studies

Imaging studies (including ^{68}Ga -PSMA-HBED-CC PET/CT and ^{177}Lu -PSMA-617 Planar/SPECT Imaging) will be performed as described in schedule as well as clinically indicated to assess disease response. In subjects enrolled in this study, the measurable disease response will be calculated using Response Evaluation Criteria in Solid Tumors (RECIST Version 1.1) with PCWG3 modifications.

Consenting subjects will undergo an optional study involving two scans with ^{68}Ga -PSMA-HBED-CC (with a minimum of 6 h and maximum of 2 days between the two injections). This cohort of patients will be analyzed to ensure that the peak standardized uptake values (including SUV_{mean} , SUV_{max} , SUV_{peak} (SUV_{peak} not applicable to brain) of the lesions in the same patient/lesion is within an acceptable range of repeatability (+/- 30%) as demonstrated by prior radionuclide repeatability studies such as FDG and FLT.

10. MEASUREMENT OF EFFECT:

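### The post-treatment option for the optional repeat 68Ga-PSMA PET/CT (Table 8, footnote n) does not fit the test-retest window in Section 9.2

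*Combined protocol and SAP*

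**What the plan says.** Four places in the protocol bear on the optional repeat scan.

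- **Table 8, footnote n.** The repeat 68Ga-PSMA PET/CT is done "prior to treatment or 6-48 hours after treatment in consenting subjects".
- **Section 9.2, Imaging Studies.** Consenting subjects have two 68Ga-PSMA-HBED-CC scans, "with a minimum of 6 h and maximum of 2 days between the two injections". The analysis is set out next: "This cohort of patients will be analyzed to ensure" that lesion uptake values in the same patient agree within ±30%.
- **Section 6.1.1, Screening Visit, procedure list.** This lists an optional repeat "injection and PET/CT prior to treatment in consenting subjects for research purposes". The required screening injection is due "at least 1 week prior to" the 177Lu-PSMA-617 infusion.
- **Section 6.1.1, closing paragraph.** This gives a shorter lead: the 68Ga procedure "should occur at least 2 days prior to Treatment Visit #1".

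Scheduled 68Ga scans occur only at screening and at the Day 85 scan (end-of-study) visit, according to Table 8, Section 6.2.5 and the Imaging Plan in 6.2.9. Reproducibility of this PET/CT is an exploratory objective (Section 1.3), and Section 2.7.5 justifies it by the lack of test-retest data.

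**The concern.** Footnote n and Section 9.2 use the same 6-to-48-hour span but start the clock at different events. In 9.2 it runs from one 68Ga injection to the next. In the second option of footnote n it runs from treatment. Because the screening injection must precede treatment by days, the two clocks cannot generally both be met.

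A repeatability study needs the two scans to differ only by measurement variation. If a dose of 177Lu-PSMA-617, which binds the same target as the tracer, is given between them, a difference in lesion uptake could reflect the scan, the treatment or both. The documents give no basis for the size or direction of a treatment effect over these hours, so it could not be removed afterwards.

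A consenting patient could therefore receive an additional tracer injection (5 ± 2 mCi at the protocol dose) and an additional PET/CT that cannot serve the objective for which they were done. Section 6 tells sites "It is very important that protocol procedures are performed at the time-points stipulated below", so a site may well follow the footnote literally.

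**Working it through.** The protocol states no figure to reproduce here. The check is interval arithmetic.

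**Inputs**

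| Quantity | Value | Source |
|---|---|---|
| Allowed time between the two 68Ga injections | 6 to 48 h | Section 9.2 |
| Minimum lead, screening 68Ga to first 177Lu dose | 48 h (2 days) or 168 h (1 week) | Section 6.1.1, closing paragraph and procedure list |
| Delay from treatment to repeat, post-treatment option | 6 to 48 h | Table 8, footnote n |
| Scan after 68Ga injection | 1 to 3 h | Section 6.1.1: "PET/CT scans will be obtained 1 to 3 hours after the infusion of" the tracer |

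**Step 1: which scan can come first.** A repeat 6 to 48 h after treatment needs an earlier 68Ga injection to pair with. Of the two scheduled injections, Day 85 (± 7 days) falls weeks after either 177Lu dose. Only the screening injection remains.

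**Step 2: shortest interval.** Interval between injections = lead + delay. Both leads are minimums, so each result is a lower bound.

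| Repeat injected | 2-day lead | 1-week lead |
|---|---|---|
| 6 h after treatment | 48 + 6 = 54 h | 168 + 6 = 174 h |
| 48 h after treatment | 48 + 48 = 96 h | 168 + 48 = 216 h |

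All four exceed 48 h.

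**Step 3: alternative readings of the footnote.**

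- *The 6 h runs to the scan, not the injection.* The injection can then be as early as 6 − 3 = 3 h after treatment. The bounds become 48 + 3 = 51 h and 168 + 3 = 171 h, still over 48 h.
- *Treatment means Treatment Visit 2.* Its earliest day is Day 14, which is 13 × 24 = 312 h after Day 1. The interval is then at least 48 + 312 + 6 = 366 h.
- *Days are counted as calendar days.* A repeat injected 6 h after treatment fits only if the true lead is at most 48 − 6 = 42 h. Two calendar days can be anything over 24 h, so a late first injection and an early treatment could allow a same-day repeat. One week in calendar days is over 6 × 24 = 144 h, so the 1-week lead never fits.

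**Step 4: what lies between the scans.** On every reading in Steps 2 and 3, at least one 177Lu-PSMA-617 dose falls between the two 68Ga injections.

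**Step 5: the pre-treatment option.** A second injection 6 to 48 h after the first, before Treatment Visit 1, meets footnote n, the 6.1.1 procedure list and 9.2. The one uncertainty is whether the minimum lead in 6.1.1 also applies to the repeat injection.

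**The case against.** **The protocol can be carried out as written.** Footnote n offers a choice, and a site that repeats the scan before treatment can satisfy footnote n, 6.1.1 and 9.2 together. This stands. A reader might infer that any site following footnote n ends up with an excluded or confounded pair. The documents do not support that, because only the second option is at fault.

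**Section 6.1.1 does not really contradict the footnote.** It is a screening list, would not be expected to show a post-treatment scan, and does not say that the repeat may be done only before treatment. This also stands. It is tempting to count 6.1.1 as a second conflict equal to the one with 9.2, but it is a mild discrepancy at most.

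**Footnote n does not mention test-retest.** The post-treatment scan might serve the other exploratory imaging objective, disease assessment before and after treatment. This is possible but not well supported. Section 4.1 assigns post-treatment assessment to the end-of-study scan, the treatment-visit lists contain no 68Ga scan in the hours after 177Lu, and no analysis is given for one. Section 9.2 is the only section that describes an optional two-scan 68Ga study, and its time span matches. If a separate scan is intended, the protocol still has to state its purpose.

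**It is probably a drafting slip.** Quite possibly the 6-48 hours was meant to follow the first injection. As written, however, it permits the post-treatment scan.

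**Conclusion.** The point holds for the post-treatment option in footnote n, and it is minor. With the leads in 6.1.1 read as elapsed time, a repeat injected 6 h or more after treatment is at least 54 h (2-day lead) or 174 h (1-week lead) after the first injection, against a maximum of 48 h.

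This rests on two assumptions: the screening scan is the first of the pair, and the repeat belongs to the 9.2 study. Footnote n states neither, but both follow from the schedule and the matching time span.

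A reader might go further and say that the post-treatment option can never meet the window. That is too strong, because calendar-day counting leaves a narrow opening for a same-day repeat under the 2-day lead. Such a pair would still mix treatment effect with scan repeatability. Nor should 96 h and 216 h be read as the longest intervals. They are the least possible for a repeat at 48 h.

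Nothing beyond the optional exploratory reproducibility objective is affected. Eligibility, the DLT and MTD determination, the PSA endpoint and the Simon two-stage design do not depend on this scan.

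**What to change.** 1. **Footnote n.** Replace the two timings with: *prior to Treatment Visit 1, with the second injection 6-48 hours after the first*.
2. **Section 9.2.** State that a pair enters the ±30% analysis only if the injections are 6 to 48 h apart and no 177Lu-PSMA-617 dose lies between them. List any post-treatment repeats already done separately.
3. **Section 6.1.1.** Make clear that the minimum lead before treatment applies to the required screening injection and not to the optional repeat. With a 48 h lead, the repeat injection could then be given up to 48 − 3 = 45 h after the first and still leave 3 h for its scan before treatment. If the lead is meant to cover both injections, the first must be scheduled earlier. For a repeat at 6 h it would be at least 48 + 6 = 54 h (or 168 + 6 = 174 h) before treatment. To use the full window it would be 96 h (or 216 h).

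The cost is one phrase in footnote n and one sentence each in 9.2 and 6.1.1. Consenting subjects still have two injections, and no scan is added. No sample size or error rate changes. The sentence in 9.2 is worth adding even if enrolment is complete, because it settles which pairs count.

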6.1.1. Screening Visit

The following procedures must be completed no more than 1 month prior to enrollment and no more than 4 weeks following enrollment.

- Informed Consent
- Demographics
- Medical History
- Previous therapy
- Surgical report will include date and type of surgery +/- lymphadenectomy
- Radiotherapy report will include modality of therapy with prescribed dose and field and dates of therapy
- Previous systemic (hormonal, chemo, other) therapy – drugs, doses, dates of therapy
- Complete Physical Exam including height and weight
- Brief Pain Inventory
- Vital Signs
- ECOG Performance Status
- CBC with differential and platelet count
- CMP (with direct bilirubin with known Gilbert's syndrome)
- PSA
- Testosterone
- CTC count via CellSearch methodology (may be collected prior to treatment C1D1, do not need to repeat if has known result within 1 month of C1D1)
- CTC for Research (may be collected prior to treatment C1D1)
- Cell-Free DNA BCT® Research blood sample (may be collected prior to treatment C1D1)
- Immune research blood sample (may be collected prior to treatment C1D1)
- CT or MRI (abdomen-pelvis), up to 1 month prior to enrollment
- Bone scan, up to 1 month prior to enrollment
- Any confirmatory tests to assess equivocal results of bone scan should also be completed within a month of enrollment
- CXR, up to 1 month prior to enrollment (CXR waived if CT chest performed)
- Single intravenous dose of ^{68}Ga -PSMA-HBED-CC ($5\pm 2\text{mCi}$ or $185\pm 74\text{MBq}$) at least 1 week prior to ^{177}Lu -PSMA-617 infusion
- ^{68}Ga -PSMA-HBED-CC PET/CT scan to confirm the PSMA expression at the tumor site(s). PET/CT scans will be obtained 1 to 3 hours after the infusion of ^{68}Ga -PSMA-HBED-CC. Optional repeat ^{68}Ga -PSMA-HBED-CC injection and PET/CT prior to treatment in consenting subjects for research purposes.
- Archival tissue for PSMA expression and genomic studies to identify DNA

damage

Screening (except required ^{68}Ga -PSMA-HBED-CC PET/CT scan) and visit #1 may occur on the same day provided results are available, all entry criteria are met, and the subject is registered on the study prior to dosing. In this instance, duplicate procedures do not need to be performed. ^{68}Ga -PSMA-HBED-CC should occur at least 2 days prior to Treatment Visit #1.

6.1.1.1. Re-screening

Subjects who are unable to complete the initial screening or are not initially eligible will be permitted undergo repeat screening (with repeat written informed consent).

6.1.2. Treatment Phase

The treatment and early monitoring phase comprises of 8 visits spanning over approximately 12 weeks.

Platelets, absolute neutrophil count, bilirubin, transaminases, and serum creatinine must be performed with results available and within range of eligibility criteria within 1 week prior to treatment initiation on C1D1.

Details for each visit are listed below:

6.1.2.1 ^{177}Lu -PSMA-617 infusion (Treatment Visit 1 Day 1)

The following procedures must be completed on the day of treatment with ^{177}Lu -PSMA-617:

- Targeted Physical Examination with vital signs and weight
- Medical History
- Brief Pain Inventory, FACT-P
- ECOG Performance Status
- CBC with differential and platelet count
- CMP (with direct bilirubin with known Gilbert's syndrome)
- PSA
- LDH
- Single intravenous dose of ^{177}Lu -PSMA-617 (Dose based on the Cohort in which the subject is enrolled)
- Adverse event evaluation
- Concomitant medications
- Concomitant procedures

As stated above, platelets, absolute neutrophil count, bilirubin, transaminases, and

renal function assessment must be available within 1 week prior to treatment on D1 and meet eligibility criteria.

For Treatment Visit 2 (**Day 15 ±1 day**), grade ≥ 2 thrombocytopenia or neutropenia within 24 hours of the second dose of ^{177}Lu -PSMA-617 requires a subject's treatment to be held until the toxicity has resolved to least grade 1. If the toxicity has not resolved after 2 weeks of monitoring, the subject's ^{177}Lu -PSMA-617 treatment will be permanently discontinued and will be termed dose-limiting toxicity

6.1.2.2 Imaging visit (Day 8 ±1)

- Planar/SPECT imaging
- Targeted Physical Examination with vital signs and weight
- Medical History
- Brief Pain Inventory, FACT-P
- ECOG Performance Status
- CBC with differential and platelet count
- CMP (with direct bilirubin with known Gilbert's syndrome)
- Adverse event evaluation
- Concomitant medications

¹⁷⁷Lu-PSMA-617 infusion (Treatment Visit 2 Day 15 ±1 day)

The following procedures must be completed on the day of treatment with ¹⁷⁷Lu-PSMA-617:

- Targeted Physical Examination with vital signs and weight
- Medical History
- Brief Pain Inventory, FACT-P
- ECOG Performance Status
- CBC with differential and platelet count
- CMP (with direct bilirubin with known Gilbert's syndrome)
- PSA
- LDH
- Single intravenous dose of ¹⁷⁷Lu-PSMA-617 (Dose based on the Cohort in which the subject is enrolled)
- Adverse event evaluation
- Concomitant medications
- Concomitant procedures
- Optional imaging will be performed on consenting subjects between Treatment Visit 1 (Between D1-D4) and/or prior to Treatment Visit #2 on (D15 ± 1)

6.1.2.2 Follow-up visits: Follow up Visit 1 (Day 22 ±3), Follow up Visit 2 (Day 29 ±3), Follow up Visit 4 (Day 57 ±3)

- Targeted Physical Examination with vital signs and weight
- Medical History
- Brief Pain Inventory, FACT-P
- ECOG Performance Status
- CBC with differential and platelet count
- CMP (with direct bilirubin with known Gilbert's syndrome)
- PSA (Follow up Visits 2 & 4)
- LDH (Follow up Visits 2 & 4)
- Adverse event evaluation
- Concomitant medications

6.1.2.3 Follow-up lab visits: Follow up Visit 3 (Day 43 ±3); Follow up Visit 5 (Day 71 ±3)

- CBC with differential and platelet count
- CMP (with direct bilirubin with known Gilbert's syndrome)

These visits may be performed with any licensed provider at any CLIA certified lab, provided that the results are available/provided to the Investigator within allowable windows.

6.1.3. Scan (initial efficacy) Evaluation Visit (Day 85 ± 7); note that these study procedures are not expected to occur on a single day)

The following procedures must be completed during the initial scan visit(s):

- Targeted Physical Examination with vital signs and weight
- Medical History
- Brief Pain Inventory, FACT-P
- ECOG Performance Status
- CBC with differential and platelet count
- CMP (with direct bilirubin with known Gilbert's syndrome)
- PSA
- LDH
- Testosterone
- CTC count via CellSearch methodology
- CTC for research
- Cell-Free DNA BCT® Research blood sample
- Immune research blood sample
- Same standard radiographic imaging modality as baseline (CT/MRI and bone scan +/- CXR)
- Single intravenous dose of ^{68}Ga -PSMA-HBED-CC ($5\pm 2\text{mCi}$ or $185\pm 74\text{MBq}$)
- PET/CT scan will be obtained between 1 and 3 hours post-injection of ^{68}Ga - PSMA-HBED-CC
- Adverse event evaluation
- Concomitant medications
- Concomitant procedures

